## **Limitations**

Parents may opt out of allowing their child to participate in the study due to the extent of the sampling. The standard of care for respiratory illnesses may include a nasal aspirate, but the additional sampling at the baseline and conclusion of the study is a deviation from standard procedure. We will, however, emphasize the ease and low-invasive nature of both the nasal aspirate specimen collections and the oscillography readings. In addition, parents may opt out of participating if their child's medical diagnosis or current health status is too emotionally overwhelming, or if they have concerns regarding the prophylactic administration of an antibiotic for 3-6 months. We will obtain respiratory samples from patients that are admitted Monday through Friday during business hours, but it will be difficult to obtain nasal samples from the Emergency Department, on weekend admissions, and afterhours. For sick episodes occurring weekends and afterhours we will collect samples on the next business day morning. Parents may also not adhere to the administering the medication/placebo three days a week.

## **Confidentiality**

Every effort will be made to protect the privacy of the subjects. Unique identifiers will not be stored in the final database that will be used for analytic purposes. Information such as age, sex, and race will be collected to examine the patterns of interaction in different demographic subgroups.

Specimens will be sent to Baylor College of Medicine for processing and testing. Specimens will be coded with study ID numbers and will not have any personal information.

Upon completion of the study, electronic data will be retained by the principal investigator ([name]) at his University of Texas Medical School office. All data

forms will be kept in a locked file cabinet and electronic files will be password protected. Subjects will not be directly identifiable. The PI, co-investigators, and designated study staff will use the information for data analysis and manuscript preparation.

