## **Study Design and Methods**

### *Overview:*

This pilot randomized control trial (RCT) will enroll 92 children from 6 months to <6 years of age that have chronic lung disease (CLD) such as bronchopulmonary dysplasia during two seasons of respiratory illnesses defined as 1st October to 31st March of each year (2015-2016 Season and 2016-2017 Season). If the minimum number of patients (n=92) in Season 1 is achieved, we will then perform an interim analysis of the data. These children will all be patients who receive their primary medical care from either the High Risk Children Clinic or the similar High Risk Infant Clinic that cares for premature infants from discharge until age 2. Clinic records will be screened to determine eligibility. Patients that have parental consent will be given a baseline EKG, a nasal aspirate, an oscillometer reading (over 2 years of age only), and a three to six month supply of either the medication or the placebo at an initial study visit. Both medications will be taken once a day for three days a week: Monday, Wednesday and Friday. The azithromycin medication will be dosed at 5 mg/kg/day. Adjustments in dosage amount will be made with any new weights obtained during the trial period. Any child that is eligible to receive Palivizumab will be given this every 28-30 days in clinic as per usual care. Patients will be followed on a monthly basis and closely monitored for adverse reactions; this will occur by phone, in clinic during their regularly scheduled appointments, and/or during any necessary illness visits. Any children with adverse reactions will discontinue the medication, but will continue to be followed clinically. At any clinic visit in which a child presents with respiratory infections, including pneumonia,

upper respiratory illness, bronchiolitis, etc., he/she will have an additional nasal aspirate and/or tracheal aspirate if applicable and an oscillometer reading (only for children >2 years) performed. At the completion of the 3-6 months treatment phase, each child will have a final nasal aspirate and/or tracheal aspirate if applicable, and an oscillometer reading performed. Data will continue to be collected for the following 2 months (April 1st to May 31st), to monitor for respiratory illnesses and possible side effects.

*Study Population:*

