## **Study Outcomes**

1. In the treatment group, we expect a 20% total reduction in face to face encounters (defined as unscheduled sick visits, emergency room visits, and hospital admissions) for respiratory symptoms with the prophylactic use of azithromycin, as compared to the control group.
  - a. In the treatment group, we expect to have a 20% decrease in the number of unscheduled sick visits due to respiratory illness during the 3-6 month study period with the prophylactic use of azithromycin, as compared to the control group .
  - b. In the treatment group, we expect to have a 20% decrease in the number of Emergency Room visits due to respiratory illness during the 3-6 month study period with the prophylactic use of azithromycin, as compared to the control group.

- c. In the treatment group, we expect to have a 20% reduction in the number of hospital admissions due to respiratory illness during the 3-6 month study period with the prophylactic use of azithromycin, as compared to the control group.
2. In the treatment group, we expect a 10% total reduction (as compared to baseline) in the level of myeloperoxidase in the nasopharyngeal secretions collected during respiratory illnesses that require a face to face provider encounter, as compared to the control group.
3. In the treatment group, we expect a 10% total reduction in the level of pro-inflammatory cytokines in the nasopharyngeal secretions collected during respiratory illnesses that require a face to face provider encounter, as compared to the control group.
4. In the treatment group, we expect a 10% reduction from baseline in the level of airway obstruction as measured by a tremoFlo Airwave Oscillometry System during the 3-6 month study period, respiratory illness and at the conclusion of the intervention phase.
5. We expect no significant difference in adverse side effects between the treatment group receiving the macrolide and the control group receiving the placebo during the 4 month study.
6. We expect the intervention to be cost-effective from a healthcare system perspective.

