## **Data Analysis Plan**

Patients will be randomized to one of two different branches by the REDCap data base randomization program. This will be a double-blind placebo controlled study. Standard frequentist and Bayesian analyses will be performed using an intent-to-treat approach. Total hospital days, total ER visits (counting one day for each ER visit), and unscheduled clinic visits (counting one day for each visit) for respiratory symptoms will be analyzed and related to treatment (Azithromycin vs Placebo), with logistic regression models and the treatment group as a covariate and random intercept to account for within patient correlation (due to multiple ED visits). To assess the probability of benefit, we will use Bayesian hierarchical models with interaction terms between treatment groups (Azithromycin vs Placebo) and predefined potential moderators. The groups will be stratified by palivizumab use and by tracheostomy on chronic mechanical ventilation. The conservative Bayesian approach of Dixon and Simon allows us to shrink the subgroup estimates to the overall mean treatment effect. For all Bayesian analyses, prior distributions for main effects will be neutral  $\sim N(0,1000)$ , and Uniform (0,1000) for SD parameters. Neutral and skeptical priors will be used for interaction terms. Point estimates of treatment effect and 95% credible intervals will be reported along with probability of treatment benefit.

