## **Sample size and power**

Based on data from our HRCC, we expect the control group to have 1.6 encounters per child-year (SD=1.66). Assuming a two-sided alpha = 0.05, a sample size of 90 (45/group) will have 80% power to detect a difference of 1 in the encounter rate between placebo and azithromycin groups (i.e., 1.6 vs 0.6 in encounter rate or 38% reduction). Power will be more limited for secondary outcomes but Bayesian analyses will provide an estimate of the probability of benefit in these outcomes.

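### The frequentist encounter model has no main effect for age or season; if age predicts visits, this gives up a modest amount of precision that could be recovered at almost no cost

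*Combined protocol and SAP*

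**What the plan says.** The overview under Study Design and Methods plans 92 children aged 6 months to under 6 years, enrolled "during two seasons of respiratory illnesses" (2015-2016 and 2016-2017). It allows for the possibility that all 92 are reached in Season 1.

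The Data Analysis Plan models respiratory encounters "with logistic regression models and the treatment group as a covariate and random intercept to account for within patient correlation". No baseline variable is listed in that model. The same section adds Bayesian hierarchical models with treatment-by-moderator interactions and gives a prior for main effects, but does not name the moderators. It names palivizumab use and tracheostomy with chronic ventilation as stratification factors, and does not place them in the frequentist model.

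As an analysis variable, age appears once, under Confidentiality: "Information such as age, sex, and race will be collected to examine the patterns of interaction in different demographic subgroups". Season of enrolment is given no analysis role.

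Two figures set the scale. Under Sample size and power, "we expect the control group to have 1.6 encounters per child-year (SD=1.66"), and "a sample size of 90 (45/group) will have 80% power to detect a difference of 1". Under Study Outcomes, "we expect a 20% total reduction in face to face encounters".

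**The concern.** With about 46 children per arm, the spread in visit rate between children is a large part of the noise. A baseline variable that explains some of that spread narrows the interval on the treatment comparison when it enters as a main effect. The plan instead gives age a role in interactions, where a trial of this size has least information.

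The documents give some reason to expect age to matter. Under Study Population, one clinic follows preterm infants for their first 2 years only. The other takes children who have already had repeated emergency visits or admissions, or an intensive care stay, in the past year. Age therefore partly marks the entry route, and one route selects on something close to the primary outcome. Season is plausible by the plan's own logic, since enrolment is built around respiratory seasons.

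Two things are at stake. One is a wider interval than necessary. The other is an awkward position if the arms happen to differ in age: adding age after unblinding would be a data-driven choice, and leaving it out would invite challenge.

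**Working it through.** **1. The plan's own figure.** Control rate 1.6, SD 1.66, difference 1.0, two-sided alpha 0.05, 45 per arm (Sample size and power).
- n per arm = 2 × (1.96 + 0.8416)² × 1.66² / 1.0² = 43.3, so 44.
- SE of the difference = 1.66 × √(2/45) = 0.350. Power at 45 per arm is 81.5% (80.7% with the t distribution).

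The stated 90 children and 80% power reproduce.

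**2. Between-child spread.** Reading 1.6 and 1.66 as the mean and SD of a yearly count, with negative binomial variation:
- k = (1.66² − 1.6) / 1.6² = 1.156 / 2.56 = 0.451.
- Log-rate variance between children = ln(1 + 0.451) = 0.373.

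**3. Share that age could explain (assumed).** Age is taken as uniform on 0.5 to 6 years, so SD = 5.5/√12 = 1.588. The visit rate is taken to fall 10% to 25% per year of age, a youngest-to-oldest ratio of about 1.8 to 4.9.
- 10% per year: log-rate SD = 0.105 × 1.588 = 0.167; share = 0.167²/0.373 = 8%.
- 25% per year: log-rate SD = 0.288 × 1.588 = 0.457; share = 0.457²/0.373 = 56%.

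**4. Precision gained, count-rate model.** Variance per arm is proportional to 1/μ + k. Counting for 5 to 8 months gives μ = 1.6 × 5/12 = 0.67 to 1.6 × 8/12 = 1.07.
- Low end: k falls to exp(0.373 − 0.028) − 1 = 0.411. Reduction = 0.040 / (1.50 + 0.451) = 2.1%, equal to 92 × (1/0.979 − 1) ≈ 2 children.
- High end: k falls to exp(0.373 − 0.209) − 1 = 0.178. Reduction = 0.273 / (0.94 + 0.451) = 19.7%, equal to 92 × (1/0.803 − 1) ≈ 23 children.

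**5. Chance age imbalance.** SE of the difference in mean age with 46 per arm = 1.588 × √(2/46) = 0.33 year. A 2-SE difference (0.66 year) multiplies the rate ratio by 0.90^0.66 = 0.933 or 0.75^0.66 = 0.827, a shift of 7% or 17%.

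**6. Cross-check on the plan's difference-in-means scale, 45 per arm.** Age uniform, rate log-linear in age, imbalance simulated and expressed as a percentage of 1.6:

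| Youngest-to-oldest rate ratio | 95% limit of imbalance | Chance of 20% or more |
|---|---|---|
| 1.5 | 4.8% | about 0% |
| 2 | 8.2% | about 0% |
| 3 | 12.9% | 0.2% |
| 4 | 16.2% | 1.6% |
| 6 | 20.8% | 6.0% |

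Equivalently, the 95% limit reaches 0.32 (20% of 1.6) only if R² = (0.32 / (1.96 × 0.350))² = 0.22.

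**7. Effect on power, by share of outcome variance explained by age (residual SD = 1.66 × √(1 − R²)).**

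| R² | Difference 1.0 | Difference 0.32 (20%) |
|---|---|---|
| 0 | 81.5% | 14.8% |
| 0.10 | 85.4% | 16.0% |
| 0.20 | 89.2% | 17.4% |
| 0.25 | 91.0% | 18.3% |

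**8. Season (illustration only).** Assume half the children in each season, simple randomisation, and a between-season rate ratio RR. The 95% limit is 2(RR − 1)/(RR + 1) × 1.96 × √(2 × 0.25/45). This is 4.6%, 8.3% and 13.8% of the control rate for RR of 1.25, 1.5 and 2.

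**The case against.** The strongest reply has five parts.

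- **No gradient is documented.** Nothing in the documents ties age or season to encounters. The upper figures need a nearly fivefold fall in rate across the age range together with an imbalance near its 95% limit. This stands, and the sizes must stay conditional.
- **Randomisation already covers chance imbalance.** The unadjusted comparison is unbiased on average and its SE includes age imbalance. With the inputs above, the SE of the log rate ratio is √(2 × 1.951/46) = 0.29 to √(2 × 1.389/46) = 0.25, so chance alone moves the ratio by 38% to 43% at its 95% limit. Age is one component of that. This stands.
- **The Bayesian models may already adjust.** They carry main effects, and age would ordinarily have one if it is a moderator. A sentence under Confidentiality about why data are collected is also not an exclusive list of uses. This stands in part: because the moderators are unnamed, nobody can tell whether age is among them, and the frequentist model still lacks it.
- **The gain was worked for another model.** The 2% to 20% assumes a count-rate model, whereas the plan names logistic regression. It also treats all between-child spread as open to age, before the stratification factors take their share. This stands.
- **Season may not vary.** If all 92 children enrol in Season 1, the term drops out. This stands.

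None of this argues against naming the covariates in advance.

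**Conclusion.** The point holds as a modest, cheap gain in efficiency. The 2% to 20% variance reduction and the 7% to 17% shift rest on assumptions: the age gradient, the uniform age distribution, the negative binomial reading of 1.6 and 1.66, and the count-rate model.

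Three stronger readings are tempting, and the documents do not support them.

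- A reader might infer that chance age imbalance could produce or cancel the expected 20% effect. That takes roughly a four- to six-fold rate ratio across the age range and an extreme draw. At ratios of 1.5 to 3 the 95% limit is about 5% to 13%.
- A reader might infer that the unadjusted test is invalid. It is not: the issue is efficiency, and bias conditional on the imbalance that happens to arise.
- A reader might infer that palivizumab stratification either captures age or isolates only the youngest children. The documents give no eligibility ages, so neither can be said.

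Adjustment also does not rescue the trial for a 20% effect. Eighty per cent power for a difference of 0.32 needs about 423 children per arm unadjusted, and about 338 if age explains 20% of outcome variance.

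**What to change.** In the Data Analysis Plan, prespecify these main effects in both the frequentist and the Bayesian primary encounter models:
- age at randomisation, as a continuous variable;
- the two stratification factors, palivizumab use and tracheostomy with chronic ventilation;
- season of enrolment (two levels), if children are enrolled in both seasons.

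State the adjusted estimand, name the Bayesian moderators, and label the age, sex and race interactions exploratory.

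The cost is a few sentences and a few model parameters, with no new data on age or season. The downside is that, if the model stays logistic, the adjusted odds ratio is conditional on the covariates and must be reported as such.

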### **Interpretation and Potential Importance of Findings**

A substantial portion of our high risk chronically ill children have some form of chronic lung disease, including patients with tracheostomies, bronchopulmonary dysplasia, and chronic respiratory failure requiring mechanical ventilation. Most of the hospital admissions in this group of patients were related to respiratory infections in children less than 6 years of age (37% during the winter season for the previous 3 years). Despite vaccination rates of nearly 100% and 24/7 access to our clinic, viral respiratory illnesses continue to cause considerable morbidity and high healthcare costs. Innovative new prophylactic treatments are needed.

With this proposal, we will determine if the prophylactic use of azithromycin will 1) reduce the number of days when unscheduled medical treatment health care related encounters was given outside the home, 2) reduce the number of emergency room visits, hospitalizations and clinic visits due to respiratory illness, 3) reduce the level of myeloperoxidase and pro-inflammatory cytokines during viral illnesses requiring face to face physician interaction, 4) demonstrate a reduction in airway obstruction as measured by an oscillometer 5) have a similar safe profile compared to the placebo, and 6) demonstrate cost-effectiveness of macrolides use. Understanding the anti-inflammatory effects of azithromycin when used as a prophylactic drug will provide important insight into the prevention of more serious sequelae of respiratory infections. In particular, this proposal will contribute to understanding disease in children ages 6 months to 6 years with chronic lung disease, a population that has a higher rate of hospitalizations for respiratory symptoms.

3. Society AT. *Statement on the Care of the Child with Chronic Lung Disease of Infancy and Childhood* 2002. Accessed 8/19/14.
